STI clinics, institutional leadership, localized epidemiology), along with indicators for study periods. Additionally, to control for temporal effects—natural improvements in PrEP implementation over time—for each client, the models will control for the time of study entry using linear and quadratic polynomials for the number of months from the start of the Standard period. With a single outcome status for each client, this controls each client's outcomes for the timing of participating during the site's PrEP implementation process. The results will indicate the average within-block change from Standard to Enhanced in the log-odds of awareness, screening, offer, initiation, and continuation. Likewise, to determine whether the effects are maintained, outcomes from the Sustainment period will be compared to the Standard and Enhanced periods.

Statistical power for Aim 1. Multilevel power analysis typically assumes interventions are at the level of individuals or groups. However, here, the intervention is time-varying. As such, power for the primary client-services level outcomes was estimated using a multi-step approach recommended by Hox³³:

First, the *total sample* of observations was computed. For client-services level PrEP outcomes (ie, awareness, screening, offer, initiations, continuation), the sample size calculation reflects the size of the site client population and the availability of donated TDF/FTC (minimum of 1064 PrEP initiators). We anticipate ~2600 MSM clients per site per year and estimate ~133 PrEP initiators per site. However, this sample size is nested, introducing dependency and decreasing the level of statistical power.

Second, to penalize the total sample for nesting, the design effect formula is reorganized (i.e. $n_{\text{eff}} = n/[1+\{n_{\text{clus}}-1\}]$) to provide the effective sample size of independent observations. Using a conservative nesting effect (i.e. =0.25 for phases/sites), the

observations provide statistical power equivalent to 32 independent observations.

Despite the large number of MSM clients each year, the effective sample reaches an upper limit of 32 due to (a) the small number of sites and (b) the large cluster size per site. However, the large cluster provides high reliability for estimated level-2 effects.

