Third, the effective sample size is used in a conventional power analysis. The results indicated that power is .80 to detect an effect of OR = 3.3 for the effect of Standard Implementation on client services outcomes. This is equivalent to a medium-to-large standardized effect of $d=0.66$, or a between-period difference in probability of 29%. For a less conservative nesting effect ($=0.10$), the sample is sufficient to detect OR=2.0, or a 16% between-period difference.

Evaluation of Specific Aim 2: To compare the time, costs, and resources required for Standard versus Enhanced PrEP implementation. The expected opportunity cost of implementation for sites will be modeled using an estimator that will identify the “best practice” implementation costs. The theoretical model assumes that sites attempt to minimize costs of implementation in order to maximize excess revenue subject to a standard economic production function. **This production function supports a dual cost function: where C_{it} represents the SIC-measured implementation costs for the i^{th} program in the t^{th} phase, X_{it} are characteristics of program i in phase t , is an i.i.d. error term, is a one-sided error term corresponding to the technical inefficiency for the i^{th} practice in phase, and represents the coefficients of the best practice (most efficient) cost function. We assume the best-practice cost function is of the CobbDouglas form, such that the log-linear transformation yields.**

With estimates of the model parameters, we will predict the best practice implementation costs and technical inefficiency costs for each program. We will also explore which program characteristics and contextual factors are associated with higher or lower estimated inefficiencies. We will include measures of the “best practice” implementation costs, technical cost inefficiency and intervention costs in a model predicting successful implementation. The aggregated cost variables will be added to linear probability models (because cost measures require a prediction substitution model) as covariates alongside SIC Duration and Proportion scores to predict the binary outcome of whether a program sustained a minimum of 1-year post Stage 8 of the SIC (Competency). Differences in use of resources will be examined between sites that sustain versus those that do not. The assessment and analysis of implementation costs will be critical for the government as they develop their plan for widespread scale-up.

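### Aim 1 power: the .80 at OR 3.3 and the 29- and 16-point detectable differences do not follow from the plan's effective sample size for the Enhanced-versus-Standard contrast, and the direction of the error is unknown

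*Combined protocol and SAP*

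**What the plan says.** All of the power text is in the SAP, under *Statistical power for Aim 1*. It works in three steps.

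- **Sample.** "We anticipate ~2600 MSM clients per site per year and estimate ~133 PrEP initiators per site". The donated drug sets a minimum of 1064 initiators.
- **Effective n.** A design effect with an ICC of 0.25 is applied, so that the "observations provide statistical power equivalent to 32 independent observations". The plan adds that "the effective sample reaches an upper limit of 32 due to (a) the small number of sites" and the large cluster size.
- **Power.** Then "the effective sample size is used in a conventional power analysis", with this outcome: "The results indicated that power is .80 to detect an effect of OR = 3.3 for the effect of Standard Implementation". That OR is equated with d = 0.66 and a difference of 29 percentage points. For an ICC of 0.10, "the sample is sufficient to detect OR=2.0, or a 16% between-period difference".

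Alpha, sidedness, the type of test, the split of the 32 between periods and the baseline rate are not given.

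The analysis to be powered is in *Model building, estimation, and significance testing* and *Evaluation of Specific Aim 1*. Dummy indicators separate the Enhanced and Observation periods from the Standard period as reference. "The results will indicate the average within-block change from Standard to Enhanced in the log-odds of awareness, screening, offer, initiation, and continuation". In addition, "the models will control for the time of study entry using linear and quadratic polynomials", and a model with site fixed effects is the check.

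**The concern.** The power calculation and the analysis do not describe the same comparison, in four respects.

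- The .80 comes from an unnamed conventional calculation on 32 observations. The effect tested is a binary period contrast, and 32 looks too few for .80 at OR 3.3.
- The 32 is the number of sites divided by the ICC. This treats all clustering as between-site variance, although the effect is measured within sites, where a stable site effect cancels.
- The time terms and the small number of sites do not enter the power step. Both cost precision.
- One effective n serves outcomes with very different denominators: about 2600 clients per site per year for an outcome such as awareness, but about 133 initiators per site for six-month continuation.

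The sentence also names the reference condition, Standard, as the effect. At stake is whether .80, 29 points and 16 points can stand as the planning statement for the main aim.

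**Working it through.** **Inputs from the plan.** 8 sites; 133 initiators per site (1064 in all); 2600 clients per site per year; ICC ρ = 0.25 or 0.10; OR 3.3 (d = 0.66, 29 points) and OR 2.0 (16 points). **Assumed:** two-sided 5%, from the planned 95% CIs; baseline 30%, back-solved in step 2.

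**1. Effective n reproduces.** n_eff = n/[1 + (m − 1)ρ].
- ρ = 0.25: 1064/(1 + 132×0.25) = 31.3; 20800/(1 + 2599×0.25) = 31.96; limit 8/0.25 = 32.
- ρ = 0.10: 74.9 and 79.7; limit 8/0.10 = 80. The plan does not state this n; it is derived here.

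**2. Effect sizes reproduce.** d = ln(OR)·√3/π gives 0.658 for OR 3.3 and 0.382 for OR 2.0. From a 30% baseline, OR 3.3 leads to 58.6% (+28.6 points) and OR 2.0 to 46.2% (+16.2 points). Both stated differences, as rounded, hold together only for baselines of 29.5–32.1%.

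**3. Power does not reproduce for an unpaired binary contrast.**
- Two-sample t-test, n per period: noncentrality d√(n/2), df 2n − 2. With 16 per period, 0.658×√8 = 1.86 on 30 df gives 0.44.
- Wald test of the log OR: SE = √[1/(n·p0·q0) + 1/(n·p1·q1)]. With 16 per period, SE = 0.745, 1.194/0.745 = 1.60, and Φ(1.60 − 1.96) = 0.36.

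| Effect | n_eff as total | n_eff per period |
|---|---|---|
| OR 3.3, n_eff 32 | 0.36–0.44 | 0.62–0.74 |
| OR 2.0, n_eff 80 | 0.32–0.39 | 0.55–0.67 |

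Each range runs from the Wald to the t result. The OR detectable with 80% power (t, two-sided) is 6.4 or 3.6 for n_eff 32, and 3.2 or 2.2 for n_eff 80.

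**4. Readings that come near .80.**
- *Paired t-test*, dz = d/√[2(1 − r)], N − 1 df. At OR 3.3 with 32 pairs, power is 0.72, 0.80, 0.84 and 0.95 for between-period correlation r = 0, 0.17, 0.25 and 0.5. At OR 2.0 with 80 pairs, about 0.80 needs r = 0.27. Using the plan's ICCs as r gives 0.84 (OR 3.3) and 0.71 (OR 2.0).
- *One-sided 5%*, n_eff per period: 0.83 and 0.78. With n_eff as the total: 0.57 and 0.52.
- *Logistic regression on a standard-normal covariate*, two-sided, 30% baseline: 0.80–0.81 at n = 31–32 for OR 3.3 and 0.79 at n = 80 for OR 2.0. Here the OR is per SD of a continuous predictor. With a binary indicator, simulation on the same n gives 0.37 and 0.31.

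**5. Why the net direction cannot be fixed.** Take the within-site log OR over 8 sites, with

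Var = V·[2s² + 1/(m·p0·q0) + 1/(m·p1·q1)]/8,

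where s² = φ·[ρ/(1 − ρ)]·π²/3, φ is the share of the clustering that is site-by-period, m is clients per site-period, and V is the variance inflation from the time terms. The documents give neither φ nor V. As an illustration, m = 1300 (half a year of all clients) or m = 44 (133/3 initiators), with a normal reference.

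For OR 3.3, ρ = 0.25, φ = 1, V = 1, m = 1300: s² = (1/3)×3.290 = 1.097; Var = (2.193 + 0.007)/8 = 0.275; SE = 0.524; Φ(1.194/0.524 − 1.96) = 0.62.

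| Case | φ=0, V=1 | φ=0.5, V=1 | φ=1, V=1 | φ=1, V=2 | φ=1, V=4 |
|---|---|---|---|---|---|
| OR 3.3, ρ 0.25, m 1300 | 1.00 | 0.90 | 0.62 | 0.36 | 0.21 |
| OR 2.0, ρ 0.10, m 1300 | 1.00 | 0.90 | 0.63 | 0.37 | 0.21 |
| OR 2.0, ρ 0.10, m 44 | 0.99 | 0.74 | 0.53 | 0.30 | 0.17 |

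Under an assumed schedule (Standard for 6, 12, 18 or 24 months, Enhanced for 12, then sustainment for 6 or 12), linear and quadratic time gives V of about 2.7–2.9. A t reference with 7 df, assumed as a small-sample allowance for 8 sites, lowers the first row at φ = 0.5 and φ = 1 (V = 1) to 0.79 and 0.50. Power thus lies well above or well below .80 according to a split the plan does not give. The second and third rows also show that the two denominators cannot share one figure.

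**The case against.** The strongest defence is that the plan describes within-block change, so a paired reading is natural, and a paired test on 32 brackets .80. This stands in part: one cannot say that no two-sided reading of 32 yields .80. But the match at OR 3.3 needs a correlation near 0.17, and OR 2.0 would need about 0.27. Neither is stated, and the same value does not serve both.

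The ICC is labelled as applying to phases and sites, which may suggest 32 per period. That would make the Standard and Enhanced total 64, whereas the plan derives 32 from the whole sample and calls it a ceiling. Even then, two-sided power is 0.62–0.74. The one-sided version comes close, but the plan commits to 95% CIs and mentions no one-sided test.

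A reader might infer that a continuous-covariate formula was used, because it matches both ORs. The documents do not say so, and the conclusion does not depend on it.

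Three further points stand. The plan attaches no power value to OR 2.0, so only its sufficiency can be questioned. The sample size was set by the client population and the donated drug, so the power figure did not drive it. The slip over Standard as the effect is one of wording, since the analysis sections make the contrast clear.

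**Conclusion.** The point holds in a limited form. Against a stated .80 at OR 3.3, the plan's own 32 observations give 0.36–0.44 (total) or 0.62–0.74 (per period) for an unpaired binary contrast at two-sided 5%. At OR 2.0, with a derived n of 80, the figures are 0.32–0.39 or 0.55–0.67. Every reading found that comes near .80 depends on an input the plan does not state. These figures rest on two-sided 5% and, for the Wald results, on a baseline of about 30%.

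Two stronger conclusions are tempting and are not supported. The first is that the trial is underpowered. The effective n is itself unsuited to a within-site contrast, the omissions pull in opposite directions, and the ICC is not split, so the net error may have either sign. The second is that a null result could not be interpreted. The planned 95% CIs will show which differences are excluded, whatever the planning power was.

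What remains is that the power and the 29- and 16-point differences are unsupported as planning figures. Severity is minor to moderate: a correction of stated figures.

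**What to change.** - Recompute power for Enhanced versus Standard as a binary period indicator under the stepped-wedge model with its time terms. Either extend the variance formula of the SAP's reference 26 to include site-by-period variance, or simulate the Aim 1 model. Make a small-sample allowance for 8 sites.
- Do this separately for the all-client outcomes and for continuation among initiators.
- State the alpha, sidedness, baseline rate and n per site-period.
- Replace the two detectable differences with a table over ICC 0.10–0.25 and a range of between-period correlation within sites (for example 0.5–1.0), labelling every assumed input.
- Name the effect as Enhanced versus Standard Implementation.

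The cost is one recalculation, one table and one rewritten paragraph. Sites, clients, outcomes and the analysis model stay as they are.

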Traditional designs—whether client-randomized or site-randomized—were not viable due to statistical power, contamination risk, and the dual focus on intervention and implementation outcomes. For instance, randomizing clients would risk contamination within sites, and randomizing sites would drastically restrict power. This

is addressed by the proposed stepped-wedge design,²⁵⁻²⁷ with all sites participating in a baseline period (Standard Implementation), experiment period (Enhanced Implementation), and post-experiment period (Observation). Blocks of sites are randomized to the *timing* of the experiment period. Because intervention condition *changes over time*, the intervention effects reflect within-block changes (e.g., between the Enhanced and Standard periods). The design is highly flexible and maximizes power, and the proposed analyses straightforwardly accommodate different data structures for client-services outcomes (Aim 1) and implementation process outcomes (Aim 2), clients that span periods, and outcomes that are both research- and site-collected.

Data structure. For Aim 1, the *client-services outcomes* are structured with repeated visits (level-1) that are nested within clients (level-2) who are nested within periods (level-3) that are nested within sites (level-4). However, for analysis, the outcomes will reflect a single status for each client (e.g., initiation of PrEP), reducing the data to a three-level structure. For Aim 2, the *implementation process outcomes* are structured with three repeated measurements (i.e., across the baseline, enhanced, and observation periods; level-1) that are nested within sites (level-2). In each case, the small number of sites will be addressed. Of note, across aims, supplementary time-to-event analyses^{28, 29} (e.g., the effect of Standard Implementation on time to client awareness) are possible by reformulating the data to client- and site-period structures. Likewise, clients will be associated with the period in which the outcome status is finalized.

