Model building, estimation, and significance testing. The nested data structures will be evaluated using mixed-effects regression models, but with 8 sites, specialized methods are required to estimate and validate the effects.^{29,30} Model estimation will utilize Bayesian Markov chain Monte Carlo (MCMC) methods.²⁷ With this approach, the results are based on a large number of replications, providing an empirically-based sampling distribution—rather than a single point estimate—for each model parameter (e.g., the effect of Enhanced Implementation). Further, the conclusions will be validated using a frequentist, fixed effects approach (i.e., dummy-coded indicators) to control for site effects.³¹ To test for within-block changes across the three periods, two dummy-coded indicators will be included to differentiate the Enhanced and Observation periods from the reference Standard period. Continuous, dichotomous, and ordered categorical outcomes will be evaluated according to Gaussian, binomial, and ordinal distributions. To evaluate the magnitude and precision of effects, 95% CIs will be computed, along with odds ratios (ORs) for non-linear outcomes. The Bayesian MCMC models will be implemented in MLwiN,²⁷ and single-level regression models will be implemented in R.³²

Evaluation of Specific Aim 1: To evaluate whether the addition of SIC-guided PrEP delivery (Enhanced Implementation) to standard health system PrEP delivery improves services outcomes, including: awareness, screening, offer, initiation, and continuation at 6 months. Although the outcomes are repeatedly monitored, each reflects a client-level status. The three-level mixed-effects regression model, with clients (level-1) within periods (level-2) within sites (level-3), will include control variables for client characteristics (e.g. age, partnership status, ethnicity [Han vs other], sexual identity) and site characteristics (e.g. staffing, collaboration history between VCT and

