Implementation outcomes. For Aim 2, with the focus on implementation process outcomes (rather than client services outcomes), the data are structured with three periods (level-1) within sites (level-2). The outcomes include the proportion of implementation activities completed, duration of activity completion, maximum implementation stage reached, and benchmarks on the Five-80s (3 consecutive months for implementation, 6 consecutive months for sustainment). The model will include key client and site characteristics, and dummy-coded indicators to differentiate the three periods. The results will indicate the difference between Enhanced and Standard in the level of each implementation outcome. As with Aim 1, the conclusions will be validated based on single-level models with fixed-effect control variables for site differences. Likewise, with the focus on achieving implementation process benchmarks, the model

will be extended to a time-to-event framework,²⁹ testing for differences between Enhanced and Standard in the time required to achieve benchmarks (adjusted for the duration of the Standard period). With the focus on implementation process outcomes, power for this aim is inherently limited. Results will focus on estimates of 95% CIs for the effect of Enhanced Implementation.

Attrition & Missing Data. Following intention-to-treat principles, sites will be retained in research measurement independently of participation in Enhanced Implementation.³⁴ Highly successful tracking and retention protocols will minimize missing data. However, some data will inevitably be missing. To address this, assumptions will be evaluated, and informed by the results, one of several approaches will be used³⁵: i) For a small proportion of missing data with evidence of Missing at Random (MAR), the data will be analyzed using the estimation procedures described above. ii) For a non-trivial amount of missing data and evidence of MAR, multiple imputation for repeated measurements will be used.³⁶ iii) For a non-random missing data mechanism, pattern mixture models will be used to identify and control the effect of the non-random mechanism.^{37, 38}

Data Analysis

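### The Aim 2 cost model treats repeated phases of one site as independent rows, so its intervals for site characteristics are too narrow if costs are correlated within site

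*Combined protocol and SAP*

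**What the plan says.** The cost model is under Evaluation of Specific Aim 2. Cost "represents the SIC-measured implementation costs for the i^{th} program in the t^{th} phase". The text then defines program characteristics, also indexed by program and phase, a noise term, an inefficiency term and coefficients. The noise "is an i.i.d. error term, is a one-sided error term corresponding to the technical inefficiency for the" program and phase in question. The model is Cobb-Douglas, so it is linear in log cost. The plan will then "explore which program characteristics and contextual factors are associated with higher or lower estimated inefficiencies", and will carry best-practice cost and inefficiency into a model of successful implementation.

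Other parts of the SAP recognise the repetition. Data structure says the Aim 2 process outcomes are "structured with three repeated measurements (i.e., across the baseline, enhanced, and observation periods; level-1) that are nested within sites (level-2"), and adds: "In each case, the small number of sites will be addressed". Implementation outcomes repeats that "the data are structured with three periods (level-1) within sites (level-2") and validates with site fixed effects. Its outcome list (proportion completed, duration, stage reached, Five-80 benchmarks) leaves out cost, which Study Design names as an Aim 2 outcome.

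**The concern.** The same eight sites recur in every phase. Wage levels, client volume or type of facility, unless fully captured by the covariates, would make a dear site dear in each phase. An error structure that ignores this counts about 24 rows as 24 independent pieces of information.

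The consequences run in opposite directions. For a characteristic that does not change within a site, the standard error is too small and chance associations look like drivers of cost. For a contrast between phases, each site is its own control, so the standard error is too large. The inefficiency score also picks up part of the site's permanent cost level, and the plan uses that score again as a predictor of success. The SAP regards the cost analysis as important for the government's scale-up planning.

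**Working it through.** **Inputs.** Eight sites (SAP, Model building). Three phases per site if phase means study period (Implementation outcomes), giving 8 × 3 = 24 rows; T = 2 (Standard and Enhanced only) and T = 8 (the eight SIC stages) are shown as alternatives. Two-sided 5% is assumed, matching the 95% intervals in the SAP. The plan states no sample size, power or error rate for the cost model, so there is no figure to reproduce.

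**Where 0.25 comes from.** It is the nesting value in Statistical power for Aim 1. With 133 clients per site, 8 × 133 / (1 + 132 × 0.25) = 1064 / 34 = 31.3. With 2600 per site, 20,800 / 650.75 = 31.96. Both agree with the plan's 32. It describes client outcomes, not cost, so here it is only one point in an assumed range.

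**Formulas.** Let ρ be the within-site correlation of log cost and σ² its variance.
- Site mean: true variance σ²[1 + (T − 1)ρ]/T, against σ²/T under independence. At T = 3 the ratio is 1.2, 1.5 and 2.0 for ρ = 0.10, 0.25 and 0.50. The 24 rows are then worth 24/1.2 = 20, 24/1.5 = 16 and 24/2.0 = 12.
- Difference between two phases over eight sites: true variance 2σ²(1 − ρ)/8, against 2σ²/8 under independence. The assumed standard error is too large by 1/√(1 − ρ): 1.15 at ρ = 0.25 and 1.41 at 0.50.

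**Simulated rejection of a true null** (least squares on log cost, 20,000 runs, T = 3):

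| ρ | Site trait, i.i.d. errors | Site trait, site means (6 df) | Phase contrast, i.i.d. errors | Phase contrast, paired |
|---|---|---|---|---|
| 0 | 5.0% | 5.1% | 5.0% | 5.1% |
| 0.10 | 7.5% | 5.1% | 4.1% | 4.9% |
| 0.25 | 10.7% | 4.6% | 2.7% | 5.3% |
| 0.50 | 17.2% | 4.9% | 0.9% | 4.9% |

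At ρ = 0.25 the site-trait rate is 7.6% with T = 2 and 24.5% with T = 8. Separate repeats at T = 3 agreed to within about one percentage point.

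**Power for a phase change of one SD** (3,000 runs): at ρ = 0.50, 50% with i.i.d. errors against 69% paired. At ρ = 0.25 there is almost no loss, 51% against 52%.

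**The plan's own second step** (T = 3, 300 runs per setting): fit a pooled normal/half-normal frontier, predict inefficiency, and regress it on a null site trait. Rejection was about 8–9%, 10–12% and 17% at ρ = 0.10, 0.25 and 0.50. Site-average predicted inefficiency correlated 0.46–0.48, 0.63–0.66 and 0.81–0.84 with the pure site effect. In 42–50% of runs across all settings the estimated inefficiency variance fell to near zero.

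**The case against.** Four objections have weight.

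- **The formula is not legible in the text available.** The absence of a site term rests on the verbal list of terms. That list survives and no item in it describes a site effect, but the finding should carry this caveat.
- **The SAP has a general rule.** Model building says: "The nested data structures will be evaluated using mixed-effects regression models, but with 8 sites" special methods are needed, with site dummies as validation. Nothing ties this to the frontier, whose own paragraph states a different error structure. If the sponsor meant it to apply, the two passages need reconciling.
- **The step is exploratory.** No test, alpha or list of characteristics is given for it. The staffing, leadership and collaboration variables named elsewhere are Aim 1 covariates. This lowers the severity but does not correct the width of any interval reported.
- **An added site term in the frontier may not be a workable cure.** In a simulated fit on 8 × 3 rows, at least one variance component collapsed in about 90% of runs. Likelihood-ratio tests inside the pooled frontier rejected anywhere from about 6% to 25% with no within-site correlation at all, depending on the set-up. Those figures therefore cannot be blamed on nesting and are not used here.

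A reader might also infer that every stable cost difference becomes inefficiency. That is too strong. Covariates can take up observed differences, and noise can absorb the rest. The i.i.d. label is attached only to the noise; no within-site structure is given for "technical inefficiency for the i^{th} practice in phase".

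**Conclusion.** The point holds as a moderate one. The cost model's stated error structure ignores the repetition of sites that the plan respects for its other Aim 2 outcomes. With three phases, the error rate for a site-fixed characteristic is about 7%, 11% and 17% at ICC 0.10, 0.25 and 0.50; a phase contrast is conservative, at about 3% and 1% for ICC 0.25 and 0.50. These sizes assume normal errors, equal correlation between phases, an ICC that the documents do not give, and phase meaning study period.

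Three stronger readings are not supported. It does not follow that findings on site characteristics will be false: the error rate rises by an amount that depends on an unknown ICC, and not at all at zero. The information is not simply eight observations in general: at ICC 0.25 the 24 rows are worth about 16, although valid inference on a site-fixed trait has only eight sites behind it. Nor do the documents show that a Standard versus Enhanced cost difference will be missed, because the frontier paragraph does not set out that contrast; the loss applies if one is fitted with these errors, and is material only at higher ICC.

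**What to change.** Under Evaluation of Specific Aim 2, replace the assumption that rows are independent across phases of a site.

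1. Make a log-cost model with a site random intercept and phase indicators the model for inference.
2. Judge site-level characteristics, including their association with estimated inefficiency, on site-level values: eight sites, 8 − 2 = 6 df for one characteristic. Site dummies cannot serve here, because they leave characteristics that are constant over time inestimable.
3. Estimate phase differences within site.
4. Keep the frontier as a descriptive secondary analysis. State that its scores may include stable site cost differences, both where they are related to characteristics and where they enter the model of successful implementation. A frontier with an added site term may not be estimable on about 24 rows, so it should not be the main analysis.
5. Define phase, since the number of rows per site drives the size of the problem.

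The change costs SAP wording and needs no new data. The price is wider intervals for site characteristics and less weight on the inefficiency scores.
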